4.2.3 Analysis of the FEV₁-related secondary variables

- Change from baseline in Trough FEV₁ on Day 2, and Day 8
- Change from baseline in Peak FEV₁ on Day 1, Day 8, and Day 14

The analyses of the above endpoints will be performed using the FAS and will be based on the same model as described in 4.2.2.

- Change from baseline in Trough FEV₁ over treatment duration (Day 1 to Day 15)
- Change from baseline in Peak FEV₁ over treatment duration (Day 1 to Day 14)

The analyses of the 2 above endpoints will be performed using the FAS. These 2 efficacy variables will be analysed by means of a mixed repeated model: fixed effects for treatment, sequence, period, and day as a repeated factor within period (Day 1, Day 8 and Day 15 (Day 14 for Peak FEV₁)) and day-by-treatment interaction; a random effect for patient (nested within sequence) will be included also. The repeated covariance structure for day will be compound symmetry; the pre-dose FEV₁ of each period being included as a covariate.

For all mixed models, the estimation method used will be Restricted Maximum Likelihood (REML). The Kenward and Roger method for computing degrees of freedom will be used. The same treatment comparisons as those for the primary variable will be performed for the secondary variables.

4.2.4 Analysis of the other FEV₁-related variables

All analyses below will be based on the FAS and will be based on the same model as described in [4.2.2](#).

- Change from baseline in FEV₁ AUC_{0-4/4h} (area under the curve for the change in FEV₁ from baseline to 4h, normalised by the time window) on Day 1, Day 8, and Day 14
- FEV₁ AUC_{0-8/8h} on Day 1, and Day 14
- FEV₁ AUC_{0-12/12h} on Day 1, and Day 14
- FEV₁ AUC_{0-24/24h} on Day 1, and Day 14

In addition, statistical analyses on the change from baseline in FEV₁ 15 min, 30 min, 1, 2, 4, 8, 23, and 23:45 hours post-dose will be presented by treatment group at Day 1 and Day 15. Also, analyses on the change from baseline in FEV₁ 15 min, 30 min, 1, 2, and 4 hours post-dose will be presented by treatment group at Day 8. All analyses will be using the FAS and will be based on the same model as described in [4.2.2](#).

Mean changes from baseline for FEV₁ will be displayed in a longitudinal plot by treatment group, where the least squares means and corresponding 95% CI from the mixed model at each time point will be displayed, separately for Day 1, Day 8, and Day 14.

Absolute FEV₁ values will be summarised by visit and time point, by treatment group using descriptive statistics. The same treatment comparisons as those for the primary variable will be performed for the secondary variables.

4.2.5 Analysis of the other efficacy variables

The change from baseline in Total BCSS score and cough, breathlessness and sputum individual domain scores assessed at Day 8 and at Day 14 (see Section [3.3.2.1](#) for definition) will be analysed by means of a mixed model: fixed effects for treatment, sequence, and period and random effect for patient (nested within sequence); the baseline will be included as a covariate.

The change from baseline in use of rescue medication at Day 8, and at Day 14 (see Section 3.3.2.4 for definition) will be analysed by means of a mixed model: fixed effects for treatment, sequence, and period and random effect for patient (nested within sequence); the baseline will be included as a covariate.

Change from baseline in CAT from Day 1 to Day 8, from Day 9 to Day 14 and during the whole treatment duration will be analysed by means of a mixed model: fixed effects for treatment, sequence, and period and random effect for patient (nested within sequence); the baseline will be included as a covariate. The same treatment comparisons as those for the primary variable will be performed for the secondary variables.

4.2.6 Exploratory outcome variables

The change from baseline in cough VAS at Day 8, and at Day 15 will be analysed by means of a mixed model: fixed effects for treatment, sequence, and period and random effect for patient (nested within sequence); baseline will be included as a covariate. The change from baseline in number of coughs as measured by cough monitoring at Day 14 will be analysed in a similar model after data transformation (a square root transformation will be applied to the counts). A summary of raw counts should also be produced.

A composite endpoint for exacerbations (moderate or severe) in COPD (COPDCompEx) will be derived and analysed. COPDCompEx combines exacerbations with events defined from patient daily diaries and dropout events.

[Redacted content with 'CCI' visible]

■ [REDACTED] CCI [REDACTED]
[REDACTED]
[REDACTED]
[REDACTED]
[REDACTED]
[REDACTED]

[REDACTED]
[REDACTED].

The analysis of this composite endpoint for exacerbations will be time to first COPDCompEx event and, for each period, it will be calculated as follows:

$$\text{Time to first COPDCompEx (of each period)} = \text{Date of first COPDCompEx (in that period)} - \text{Date of Day 1 (of each period)} + 1$$

For each period, if a patient presents either an exacerbation as described above, or any diary event meeting the threshold and slope criteria, or drops out, COPDCompEx will be 1 (otherwise it will be 0). For those patients with COPDCompEx=1 the date when the event (either exacerbations, diary events or dropouts) occurred will be also recorded. Patients with COPDCompEx=0 in a particular period, will be considered as censored in that period. The date of censoring will be defined as last day of treatment in that period (or date of withdrawal if not judged to be a dropout due to lack of efficacy, whichever is sooner).

Time to to first COPDCompEx event will be analysed using a Cox's proportional hazards model with factors for treatment, sequence, and period. Patient will be fitted as as a clustering factor. Hazard ratios with 95% CIs will be presented, for the comparisons of AZD8871 600 µg to Anoro® Ellipta® and to Placebo.

Time to to first COPDCompEx event will be summarized in a table including the following summary statistics: the number of subjects in the analysis, the percentage of patients with events, the mean time to event, and the median time to event with 95% CI, for each treatment (AZD8871 600 µg Anoro® Ellipta® and Placebo). In addition, a Kaplan-Meier plot will be provided.

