3.3.2.2 COPDCompEx, Cough VAS and Cough Monitoring

A composite endpoint for exacerbations (moderate or severe) in COPD (COPDCompEx) will be derived and analysed. COPDCompEx combines exacerbations with events defined from patient daily diaries. The definitions for the different types of events are as follows:

- Exacerbations: episodes leading to one or more of the following; hospitalisation, emergency room visit, treatment with oral corticosteroids, or treatment with antibiotics.
- Diary events: defined by threshold and slope criteria using the following diary variables: individual domains of the breathlessness, cough, and sputum scale and rescue medication use.
- Dropouts: Dropouts due to lack of efficacy (if possible to judge) occurring during treatment periods.

The following COPD and cough variables will be assessed:

- Change from baseline in cough VAS on Day 8 and Day 15
- Change from baseline in number of coughs as measured by cough monitoring on Day 14
- Time to first COPDCompEx.

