5. INTERIM ANALYSES (NOT APPLICABLE)

6. CHANGES OF ANALYSIS FROM PROTOCOL

Change in the analysis set used:

All demographic and baseline characteristics will be analysed using the full analysis set instead of the safety population.

Change in definition of baseline for vital signs, laboratory variables including i-STAT glucose and potassium and ECG variables:

Baseline is defined as the last assessment made before the first dose of IP in each period instead of the value obtained prior to the morning IP administration on day 1 of Visit 3

For HR, and QTcF parameters:

Analyses of change from baseline at each day and timepoint within day will be performed instead of the analysis of AUC₀₋₄ at Day 1, Day 8, and Day 14 and AUC₀₋₂₄ at Day 1 and Day 14. No formal analysis of other ECG parameters will be performed.

Dropouts due to lack-of-efficacy during treatment periods added as a COPDCompEx event.

Additional analysis on FEV1:

Statistical analyses on the change from baseline in FEV1 15 min, 30 min, 1, 2, 4, 8, 23, and 23:45 hours post-dose will be presented by treatment group at Day 1 and Day 15.

Also, analyses on the change from baseline in FEV1 15 min, 30 min, 1, 2, and 4 hours post-dose will be presented by treatment group at Day 8.

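### The COPDCompEx event flag in SAP 4.2.6 has no lack-of-efficacy qualifier on dropout, which contradicts the endpoint definition and the censoring clause in the same paragraph

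*SAP*

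**What the plan says.** The protocol (9.4.4) builds COPDCompEx from exacerbations and diary events only. The SAP adds a dropout component and describes it in four places.

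- **SAP 3.3.2.2, definition:** "Dropouts: Dropouts due to lack of efficacy (if possible to judge) occurring during treatment periods".
- **SAP section 6, declared change from protocol:** "Dropouts due to lack-of-efficacy during treatment periods added as a COPDCompEx event".
- **SAP 4.2.6, flag rule:** for each period, a patient who has an exacerbation or a qualifying diary event, "or drops out, COPDCompEx will be 1 (otherwise it will be 0". The next sentence has the date of the event recorded and names dropouts, again without a reason, as one of the event types.
- **SAP 4.2.6, censoring rule:** "Patients with COPDCompEx=0 in a particular period, will be considered as censored in that period". The censoring date is the last day of treatment in the period, "or date of withdrawal if not judged to be a dropout due to lack of efficacy, whichever is sooner".

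The flag and its date feed a Cox model with treatment, sequence and period as factors and patient as cluster. They also feed a summary table (percentage with events, mean and median time) and a Kaplan-Meier plot.

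**The concern.** The flag rule is the sentence a programmer would code from, and it is the one that leaves out the restriction. The censoring clause cannot repair it, because it applies only to patients already flagged 0. Someone who withdraws for an adverse event or by personal decision has by then been flagged 1.

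Two programmers could therefore build different event data sets from the same SAP. Under the literal one, withdrawals unrelated to efficacy enter the hazard ratios, the percentage with events and the Kaplan-Meier curves as treatment failures. Protocol 7.1 lists many such reasons: patient decision, adverse event, non-compliance, and blood pressure, laboratory and ECG criteria. In the visible SAP, this composite is the only exacerbation-type endpoint with a specified treatment comparison.

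**Working it through.** **1. The rules applied to one patient.** Take a patient who withdraws on Day d of a treatment period for a reason other than lack of efficacy, with no earlier exacerbation or diary event.

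| Rule | Status | Time |
|---|---|---|
| 4.2.6 flag rule, read literally | event (flag 1) | d − 1 + 1 = d days |
| 3.3.2.2 and section 6 | not an event | – |
| 4.2.6 censoring clause, if it were reached | censored | date of withdrawal |

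Under the literal flag, the part of the censoring clause about other withdrawals applies to nobody. Under the restricted definition, every sentence has an effect. A dropout whose reason cannot be judged is also split: an event under the flag rule, censored under the clause.

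**2. The plan's own figures.** Protocol 9.2 and SAP 1.3 give 54 evaluable patients and 25% dropout. 54/(1 − 0.25) = 72, as stated, so 72 − 54 = 18 dropouts are expected. A paired t-test with a 100 mL difference and an SD of differences of 220 mL has 90.6% power at n = 54, against the stated 90%. These figures rest on trough FEV₁. No event count or power is stated for COPDCompEx.

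**3. How many dropouts could be misclassified.** The bounds are 0 and 18. Three things bring the number below 18:

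- Some dropouts fall in wash-out. Treatment lasts 3 × 14 = 42 days, and the two wash-outs last 84 to 98 days. A patient who fails the FEV₁ stability check at Visit 6 or 9 leaves before that period's first dose (protocol 8.1.2).
- Some are for lack of efficacy and are proper events.
- Some follow an event already counted. A moderate or severe exacerbation is itself a withdrawal criterion (protocol 7.1).

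Two scenarios, both assumptions:

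- *Proportional to time:* 18 × 42/(42 + 84) = 6 on treatment, or 2 per treatment; 2/72 = 2.8%.
- *All 18 on treatment, none for lack of efficacy, none with an earlier event:* 18/3 = 6 per treatment; 6/72 = 8.3%. This is the upper limit for an even spread.

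**4. Effect on a risk ratio.** Let p be the comparator's true 14-day event risk (assumed), d the misclassified proportion, equal in both arms, and 0.50 the true ratio (assumed). Observed ratio = (0.5p + d)/(p + d).

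| p | d = 2.8% | d = 8.3% |
|---|---|---|
| 5% | 0.68 | 0.81 |
| 10% | 0.61 | 0.73 |
| 15% | 0.58 | 0.68 |

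For p = 10%: (0.050 + 0.028)/(0.100 + 0.028) = 0.61, and (0.050 + 0.083)/(0.100 + 0.083) = 0.73.

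**5. The same on the hazard scale, since the plan uses a Cox model.** Assume constant hazards, a true hazard ratio of 0.60 against placebo, and non-efficacy dropout of 3% or 8% per period in both arms. With cumulative hazards H = −ln(1 − risk), the observed ratio is (0.60·H_event + H_drop)/(H_event + H_drop). At 10% placebo risk it is 0.69 or 0.78; at 20% it is 0.65 or 0.71. The direction is the same.

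**The case against.** The strongest reply is that the SAP, read as a whole, is clear. The definition, the declared change and the censoring clause all carry the restriction, and only one phrase omits it. The censoring clause makes sense only if other withdrawals are not events. In addition, a redacted block in 4.2.6 comes just before the derivation, and Appendix A is redacted too; either may restate the component. Much of this stands. The intent is evident, and the redacted text cannot be checked. But the visible flag sentence carries neither a qualifier nor a cross-reference for dropout, and the conflict between visible sentences remains whatever the redactions contain.

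A reader might infer more than the documents support:

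- *That the SAP plans to count every dropout as an event.* It does not; it contradicts itself, and three of its four statements say otherwise.
- *That 8.3% per treatment is the expected contamination.* That figure needs all three conditions in the second scenario of step 3, and none is stated or likely to hold in full.
- *That the error works against the active drugs because tolerability withdrawals are commoner on them.* No section supports this. Protocol 2.3 reports AZD8871 as well tolerated. The dilution shown needs only similar dropout across treatments; if dropout differed, the bias could go either way.
- *That listing "the mean time to event" is itself an error under censoring.* The SAP does not say which estimator is meant, and a Kaplan-Meier-based mean is possible. Event risk is already covered by the percentage with events, the plot and the hazard ratios. At most, the estimator should be named.

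**Conclusion.** The concern holds as an internal contradiction. Followed literally, the flag rule in SAP 4.2.6 gives events that the SAP's own definition excludes, and the clause meant to censor those patients is never reached. If non-efficacy dropout is similar across treatments, the hazard ratios move towards 1.

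The size cannot be fixed from the documents: 0 to 18 dropouts could be affected. The range of 0.61 to 0.73 for a true 0.50 rests on an assumed 10% comparator risk, 2 to 6 misclassified dropouts per treatment, an even spread over treatments and a denominator of 72.

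The consequence is limited. COPDCompEx is exploratory, the SAP describes the study's purpose as estimation, and the trough FEV₁ analysis and the sample size do not depend on it.

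**What to change.** In SAP 4.2.6:

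1. Qualify the dropout condition in the flag rule so that it covers only dropout due to lack of efficacy during the treatment period.
2. Put the same qualifier on dropouts in the sentence that records the event date.
3. State that all other withdrawals, including those whose reason cannot be judged, have flag 0 and are censored at the withdrawal date if they had no earlier event in that period.

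Optionally, name the estimator for the mean time to event and its restriction time (Day 14).

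The cost is a few words in one SAP section before unblinding. It needs no new data and no change to the sample size or the primary analysis.

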4.3 Analysis of pharmacokinetic variables

4.3.1.1 Descriptive statistics

All PK summary statistics and inferential statistics will be based on the PKs.

A listing of all available PK blood sample collection times as well as derived sampling time deviations will be provided.

AZD8871 and LAS191861 plasma concentrations will be listed by subject and time-point for the relevant treatment period and treatment sequence.

Plasma concentrations for AZD8871 and its primary metabolite (LAS191861) will be summarised after the first dose of AZD8871 on Day 1 and after QD multiple doses on Day 14 using descriptive statistics (n, n below LLOQ, geometric mean (gmean), $gmean + gSD$, $gmean - gSD$, geometric coefficient of variation [gCV%], minimum, median and maximum) based on the PKS.

The statistics for geometric mean, geometric mean \pm geometric SD and geometric CV% will be calculated as follows:

Geometric mean: Calculated as $\exp[\mu]$

Geometric mean \pm geometric SD: Calculated as $\exp[\mu \pm s]$

Geometric CV% : Calculated as $100 \times \sqrt{\exp(s^2) - 1}$

For the geometric mean, geometric mean \pm geometric SD and geometric CV%, the following holds:

- s is the arithmetic standard deviation of the natural log-transformed variable
- μ is the arithmetic mean of the natural log-transformed variable
- \exp denotes the power function based on the natural base e

Individual concentrations below the Lower Limit of Quantification (LLOQ) of the bioanalytical assay will be reported as NQ in the listings with the LLOQ defined in the footnotes of the relevant TFLs. Individual plasma concentrations that are Not Reportable will be reported as NR and those that are missing will be reported as NS (No Sample) in the listings. Plasma concentrations that are NQ, NR or NS will be handled as follows for the provision of descriptive statistics:

- Any values reports as NR or NS will be excluded from the summary tables and figures.
- At a time point where less than or equal to 50% of the values are NQ, all NQ values will be set to the LLOQ, and all descriptive statistics will be calculated accordingly.
- At a time point where more than half (but not all) of the values are NQ, the $gmean$, $gmean + gSD$, $gmean - gSD$ and $gCV\%$ will be set to Not Calculated (NC). The maximum value will be reported from the individual data, and the minimum and median will be set to BLQ.

- If all values are BLQ at a time point, no descriptive statistics will be calculated for that time point. The gmean, minimum, median and maximum will be reported as BLQ and the gCV% and gmean + gSD and gmean – gSD as NC.
- The number of BLQ values (n below LLOQ) will be reported for each time point.

Three observations > LLOQ are required as a minimum for a plasma concentration to be summarized. Two observations > LLOQ are presented as minimum and maximum with the other summary statistics as NC.

Plasma concentrations that are NQ will be handled as follows for display in figures:

- For gmean concentration-time plots: NQ concentrations will be handled as described for the descriptive statistics. If this handling results in a geometric mean of "NQ", then the value plotted at that time-point will be zero for linear plots and set to missing for semi-logarithmic plots. Any gmean±gSD error bar values that are negative will be truncated at zero on linear concentration-time plots and omitted from semi-logarithmic plots
- For individual plots and combined individual plots: NQ values prior to the first quantifiable concentration in that profile will be set to zero (linear plots only); after the first quantifiable concentration of the profile any NQ values will be set to missing

Subjects who reported Day 1 pre-dose concentrations > 5% of C_{max} may be excluded from the Day 1 PK analysis and/or statistical analyses.

Plasma PK parameters for AZD8871 and its primary metabolite (LAS191861) will be summarised using descriptive statistics as follows:

- C_{max}, C_{avg}, AUC₍₀₋₂₄₎ and AUC_{last}: present n, gmean, gmean+gSD, gmean-gSD, gCV(%), median, min and max.
- All parameter ratios (i.e. Rac values and metabolite to parent ratios): present n, gmean, gCV(%), mean, SD, median, min and max.
- %Fluc: present n, mean, SD, median, min and max.
- t_{max} and t_{last} : present n, median, min and max.

Three values are required as a minimum for PK parameters to be summarized. Two values are presented as a min and max with the other summary statistics as NC.

For concentration data, the listings will be presented to the same number of significant figures as the data received from the bioanalytical laboratory; for PK parameters, the listings will be presented according to the following rules:

- C_{\max} will be presented to the same number of significant figures as received from the bioanalytical laboratory.
- t_{\max} and t_{last} will be presented as received in the data, usually to 2 decimal places
- AUC_{last} , $AUC_{(0-24)}$, C_{avg} , accumulation ratios and metabolite to parent ratios and %Fluc and will be presented to 3 significant figures

For concentration data all descriptive statistics will be presented to 4 significant figures with the exception of the minimum and maximum which will be presented to 3 significant figures. For PK parameter data the descriptive statistics will be presented according to the following rules:

- C_{\max} , AUC_{last} , $AUC_{(0-24)}$, C_{avg} , Rac ratios, metabolite to parent ratios and %Fluc descriptive statistics will be presented to 4 significant figures with the exception of the minimum and maximum which will be presented to 3 significant figures
- t_{\max} and t_{last} all descriptive statistics will be presented as received in the data, usually to 2 decimal places

PK concentration and parameter data for patients excluded from the PKs will be included in the data listings, but not in the descriptive or inferential statistics or in mean figures or combined individual figures.

Individual plasma concentrations versus actual elapsed time after dose will be plotted on both linear and semi logarithmic scales for AZD8871 and LAS191861 separately with the Day 1 and Day 14 data overlaid on the same plot. Combined individual plasma concentrations will be presented on both linear and semi logarithmic scales with separate plots for each analyte and PK day (Day 1 and Day 14).

Figures for the gmean concentration-time data (with gSD error bars) will be presented, on both a linear and semi-logarithmic scales by analyte, with Day 1 and Day 14 overlaid on the same plot.

To evaluate any potential carryover effect in the study due to AZD8871 treatment, Day 1 predose concentrations for AZD8871 and LAS191861 in those periods preceded by AZD8871 treatment will be also listed. These data however, will not be summarized.

4.3.1.2 Statistical analysis of accumulation in AZD8871 exposure (C_{\max} and $AUC_{(0-24)}$) following multiple doses

$AUC_{(0-24)}$ and C_{\max} at Day 1 and Day 14 will be analysed by means of a linear mixed-effect model with the logarithm of the PK parameters as the response variable and sequence, period,

and day as fixed effects, random effect for patient nested within sequence and day being treated as a repeated effect within patient, the covariance structure being assumed to be compound symmetry. ADZ8871 accumulation will be evaluated by comparing $AUC_{(0-24)}$ (Day 14) with $AUC_{(0-24)}$ (Day 1) and C_{max} (Day 14) with C_{max} (Day 1) in the same model. From these models, least squares (LS) means together with 95% CI for Day 1 and Day 14, and LS means together with 90% CI for the difference for Day 14 versus Day 1 will be obtained. The results will be transformed back to the original scale by exponentiation to provide estimates of geometric LS means, geometric LS mean ratios for Day 14/Day 1 and corresponding CI.

